### **3.5.5.3 Analysis of Vaccine Safety**

The safety follow-up period will occur for at least 1 year following the last VZV vaccination. Safety and tolerability of V212 will be assessed by evaluation of all relevant safety parameters, focusing on the 28-day follow-up period after any vaccination. The following safety analyses will be evaluated for the HM and STM populations separately.

The primary safety endpoint of the study will be based on the incidence of SAEs observed during the period up to 28 days Postdose 4 in each vaccination group. Two-sided 95% CI on the proportion of any SAE will be provided for each vaccination group based on the exact binomial distribution [19]. To provide an overall assessment, safety measures such as the proportion of patients with (1) any adverse experience, (2) any injection-site adverse experience, (3) any systemic adverse experience, (4) any SAE, (5) any vaccine-related SAE, and (6) any discontinuation due to an adverse experience will be summarized for both vaccination groups (across any vaccination dosing period and by each vaccination dosing period). The risk differences on these overall safety parameters between the two groups and the corresponding two-sided 95% CI on the risk difference will be provided using the stratified asymptotic methods proposed by Miettinen and Nurminen [20].

To assess the risks of the adverse experiences temporally associated with vaccination, a multi-tiered approach will be used for the analysis of specific safety parameters.

For Tier-1 adverse experiences, risk differences between the two groups, corresponding two-sided 95% CI on the risk difference, and the p-value for the test of significant risk difference will be provided. The corresponding p-value will be based on the normal approximation for testing two independent binomial proportions at the two-sided 0.05 level adjusting for stratification factors. The risk difference and 95% CI will be calculated using the methods proposed by Miettinen and Nurminen [20]. Tier 1 adverse experiences include (1) systemic adverse experiences prompted for on the VRC, including varicella/varicella-like or an HZ/HZ-like rash occurring after any study vaccination through 28 days Postdose 4, (2) injection-site complaints prompted for on the VRC, such as redness, swelling, and pain/tenderness/soreness occurring Day 1 through Day 5 after any vaccination, and (3) elevated temperature ( $\geq 100.4^{\circ}\text{F}$  [ $\geq 38.0^{\circ}\text{C}$ ]), after any study vaccination through 28 days Postdose 4.

Additional summaries on Tier-1 safety parameters will also be provided by the dosing period..

For Tier-2 adverse experiences, risk differences between the two groups and the corresponding two-sided 95% CI on the risk difference will be provided using the methods proposed by Miettinen and Nurminen. This Tier-2 approach will be applied to the proportions of any other injection-site adverse experiences or systemic adverse experiences after any study vaccination through 28 days Postdose 4 that are not prompted for on the VRC but occurred in at least 1% of the patients in either treatment group.

Additional summaries on Tier-2 safety parameters will also be provided by the dosing period, and gender in each vaccination group.

Tier 3 adverse experiences will include summaries for any other adverse experiences after any study vaccination through 28 days Postdose 4.

The rate of SAEs, vaccine-related SAEs and death that occur throughout the entire study follow-up period will also be summarized per 1000 person-years of follow-up by vaccination group, to account for potential differential follow-up time by vaccination group. The probability of mortality will also be estimated and displayed by the Kaplan-Meier curve for each vaccination group. Risk difference and the corresponding 95% CI of these long-term safety parameters between the vaccine group and placebo group will be provided using an asymptotic method for differences of 2 independent Poisson rates. Mortality and SAEs, including vaccine-related SAEs will also be listed by patient with more detailed information.

SAEs and Tier-1 adverse experiences during the primary safety follow-up period will be summarized by body system.

Summaries of varicella/varicella-like or an HZ/HZ-like rash occurring during the primary safety period, through 28 days postvaccination 4, will be provided by vaccination group and by lesion type (wild type versus vaccine strain) determined by PCR. Occurrence of opportunistic infections during the primary safety period (from Day 1 to Day 28 Postdose 4) will also be summarized as adverse experiences. Occurrence of opportunistic infections and recurrence of disease that are SAEs at any time during the study will also be summarized.

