## **3.5 STATISTICAL ANALYSIS PLAN**

This section outlines the statistical analysis strategy and procedures for the study. If, after the study has begun, but prior to any unblinding, changes are made to primary and/or key secondary hypotheses, or the statistical methods related to those hypotheses, then the protocol will be amended (consistent with ICH Guideline E-9). Changes to exploratory or other non-confirmatory analyses made after the protocol has been finalized, along with an explanation as to when and why they occurred, will be listed in the Clinical Study Report (CSR) for the study. Post hoc exploratory analyses will be clearly identified in the CSR. No separate Statistical Analysis Plan (SAP) will be issued for this study.

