### **3.5.3.3 Safety**

The minimum safety follow-up period is at least 1 year following the last study vaccination.

The primary safety endpoint of the study will be based on the incidence of SAEs observed during the period up to 28 days Postdose 4 in each vaccination group. Key safety measures for an overall assessment include proportions of patients with (1) any adverse experience, (2) any injection-site adverse experience, (3) any systemic adverse experience, (4) any SAE, (5) any vaccine-related SAE, and (6) any discontinuation due to an adverse experience. Other key safety parameters include proportions of patients reporting the following adverse experiences:

1. SAEs observed Vaccination Day 1 through 28 days Postdose 4.
2. VRC-prompted systemic adverse experiences (including non-injection site varicella-like rash or HZ-like rash) following any vaccination of V212 or placebo through 28 days Postdose 4.
3. VRC-prompted injection site adverse experiences (such as redness, swelling, and pain/tenderness/soreness) Day 1 to Day 5 following any vaccination of V212 or placebo.
4. Elevated temperature ( $\geq 100.4^{\circ}\text{F}$  [ $\geq 38.0^{\circ}\text{C}$ ] oral or oral equivalent) following any vaccination of V212 or placebo through 28 days Postdose 4.
5. Any other systemic and injection-site adverse experiences not prompted for on the VRC following any vaccination with V212 or placebo through 28 days Postdose 4.
6. SAEs observed at any time for the duration of the study.

For other adverse experiences not prompted for on VRC, the safety parameters include the incidences of injection-site adverse experiences or systemic adverse experiences after any study vaccination through 28 days Postdose 4 occurring in at least 1% of the patients in either vaccination group.

Incidence of varicella/varicella-like or an HZ/HZ-like rash occurring during the period up to 28 days Postdose 4 will be summarized by skin lesion type (wild type versus vaccine strain) determined by PCR. The rate of SAEs, vaccine-related SAEs and death during the whole period of the study will be summarized per 1000 person-years of follow-up.

The safety analyses will be evaluated for the HM and STM populations separately

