### **3.5.5.1.3 Analysis of Vaccine Efficacy on Exploratory Endpoints**

The following exploratory efficacy analyses will be conducted for the STM and HM populations separately.

To evaluate the vaccine effect on the severity of HZ pain among HZ cases, the severity-by-duration of HZ pain (calculated as the area under the “worst pain in the last 24 hours” versus time curve) will be summarized by vaccination group on a MITT population. To compare the mean severity-by-duration measure of HZ pain among patients who develop HZ between the two vaccination groups, an analysis of covariance (ANCOVA) model adjusting for similar covariates as for the primary efficacy analysis will be used to get the point estimate and a bootstrap method will be used to obtain 95% CI of HZ severity-by-duration scores difference between the vaccination groups. Additional exploratory analysis may include the use of antiviral drug initiated within 72 hours of HZ rash onset (Yes versus No) as an additional covariate.

In addition, the mean and median duration of HZ pain (time from rash onset to the first visit when pain score became persistently < 3) will be provided by vaccination group. The mean HZ pain score, the numbers of lesions, dermatomes and extent of rash (defined as the maximum area of the HZ rash at each HZ follow-up visit), the mean ADLI score and the mean EuroQoL score will be summarized by vaccination group. ANCOVA models will also be used to compare these mean scores between the two vaccination groups at each HZ follow-up visit. In addition, the score-by-duration of ADLI and score-by-duration of general health status score in EuroQoL over 6 months post-HZ onset (calculated by area under the ADLI curve and general health status score curve, respectively) will be summarized by vaccination group and compared by ANCOVA model.

Poisson regression with generalized estimating equations will be used to evaluate the effect of the vaccine on the rates of non-protocol mandated health care utilization and work loss. If the counts of health care contacts in each treatment group are less than 10, then an exact binomial method will be used to calculate the CIs rather than generalized estimating equations.

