### 3.5.6 Multiplicity

With the decision made from the first interim futility analysis (provided in Sections 1.3 and 1.4), there is only one efficacy analysis performed for the primary efficacy hypothesis in the STM population. As no population enrichment is planned, no multiplicity adjustment will be made for primary efficacy analysis in the STM population and the primary efficacy hypothesis will be tested at one sided  $\alpha=0.0125$ .

No multiplicity adjustment will be made for the analyses related to the secondary objective and exploratory objectives, including any analyses related to immunogenicity, due to their exploratory nature.

For comparisons of adverse experiences between the vaccine and placebo groups, the goal is to investigate if there exists an overall trend of risk difference between the 2 groups. It is recognized that there exists a multiplicity issue for conducting multiple comparisons on these items, with each comparison being performed at the two-sided 0.05 level (corresponding to the 95% CI). Since the overall significance level for these comparisons will be much  $>0.05$ , caution should be exercised when interpreting the results.

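### Whole-study SAE rate difference: the plan names neither the numerator nor the time at risk, and the plain Poisson interval is too narrow on one reading and generally too wide on another

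*Combined protocol and SAP*

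**What the plan says.** Section 3.5.5.3 states: "The rate of SAEs, vaccine-related SAEs and death that occur throughout the entire study follow-up period will also be summarized per 1000 person-years". The stated purpose is to allow for unequal follow-up between groups. The difference and its 95% CI "between the vaccine group and placebo group will be provided using an asymptotic method for differences of 2 independent Poisson rates". The text calls this a risk difference although the quantities are rates.

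Section 3.5.3.3 repeats the person-year rate, also without a counting unit. Separately it says "Other key safety parameters include proportions of patients reporting the following adverse experiences", and the list that follows ends with "SAEs observed at any time for the duration of the study". The summary in 2.7.3 adds nothing on the unit.

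SAEs are collected from consent to the end of the study, whatever their cause (3.4.1.2 and 3.4.5.1), so one patient can contribute several. For HZ, 3.5.5.1 fixes a rule (first episode only). No such rule is given for SAEs. Section 3.5 says that no separate SAP will be issued.

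**The concern.** A Poisson variance for a rate sets the variance of the count equal to its mean. That holds for repeated SAEs only if all patients share one underlying rate. In patients on chemotherapy for solid tumours, SAE propensity plausibly differs between patients. Repeat events then cluster, and the Poisson variance is too small.

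If each patient is counted at most once but total follow-up stays in the denominator, the count behaves more like a binomial, and the Poisson variance is too large. The method is close to right for all SAEs without between-patient variation, or for first SAEs with person-time stopped at the event. The plan specifies neither.

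At stake is the between-group interval that 3.5.5.3 sets out for all-cause SAEs over the whole study. Too narrow an interval excludes zero too often and may suggest harm or benefit that is not there; too wide an interval may hide a difference. Leaving the unit open until after unblinding also adds avoidable discretion.

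**Working it through.** **Inputs from the documents.** 1348 STM patients per group (3.5.7.2); enrolment over 36 months and 30% total loss (3.5.7.1); about 5 years from first patient (1.4), so administrative follow-up of 2 to 5 years. The plan states no figure for the long-term SAE interval, so none can be reproduced. As a check on the group size, two nearby figures in 3.5.7.2 do reproduce: 1 − (1 − 1/838)^1348 = 80.0% and 1 − (1 − 1/1943)^1348 = 50.0%.

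**Assumptions, since the documents give no values.** SAE rate r = 0.1, 0.2 or 0.3 per person-year; gamma-distributed patient propensity with mean 1 and variance k; no true group difference; uniform accrual; loss hazard 0.103 per year, which yields 30% loss. Follow-up T then has E[T] = 2.91 years and E[T²]/E[T] = 3.44 years, or 1348 × 2.91 ≈ 3,920 person-years per group.

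**All SAEs over total follow-up.** The true-to-Poisson variance ratio is V = 1 + k·r·E[T²]/E[T]. Coverage of the nominal 95% interval is 2Φ(1.96/√V) − 1.

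| r | k | V | Coverage |
|---|---|---|---|
| any | 0 | 1.00 | 95% |
| 0.1 | 0.5 | 1.17 | 93% |
| 0.1 | 1 | 1.34 | 91% |
| 0.2 | 0.5 | 1.34 | 91% |
| 0.2 | 1 | 1.69 | 87% |
| 0.3 | 1 | 2.03 | 83% |
| 0.3 | 2 | 3.06 | 74% |

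Simulation with 10,000 replicates per setting gave 94.6% (r = 0.2, k = 0), 90.7% (0.2, 0.5), 86.6% (0.2, 1), 82.1% (0.3, 1) and 73.3% (0.3, 2). At r = 0.2 zero is therefore wrongly excluded in about 9% (k = 0.5) to 13% (k = 1) of trials instead of 5%.

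**Loss linked to propensity.** When loss or death is made proportional to SAE propensity, still 30% in total, coverage at r = 0.3 rises from 82% to 87% (k = 1) and from 73% to 82% (k = 2).

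**Patients with an SAE over total follow-up.** With fixed follow-up, V = 1 − p, where p is the proportion with at least one SAE. At r = 0.2 and k = 1, p = 0.35, so √V = 0.81 and coverage is about 98.5% (simulated 98.7%). Over the settings run it was about 96% to 99.8%.

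**First SAE with person-time stopped.** Simulated coverage was 93% to 95%, falling to about 91% with strong propensity-linked mortality.

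**Patient-level robust variance.** Per group this is Σ(xᵢ − r̂Tᵢ)² / (ΣTᵢ)², where xᵢ is the patient's count and r̂ the group's rate. Coverage was about 94% to 96% for either numerator over total follow-up.

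**Width at r = 0.2.** The Poisson half-width is 1.96 × √(2 × 0.2/3,920) = 19.8 per 1000 person-years. The robust half-width for all SAEs is 19.8 × √1.34 = 22.9 at k = 0.5 (+16%) and 19.8 × √1.69 = 25.7 at k = 1 (+30%).

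**Other endpoints.** The Poisson method covered 94% to 95% for death (assumed hazard 0.05 to 0.2 per year) and 95% for vaccine-related SAEs at an assumed 0.003 per person-year. Only the STM group sizes were examined.

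**The case against.** The strongest reply is that no numerical error in the plan has been shown. The documents fix neither the counting unit nor any SAE rate or dispersion, so every coverage figure rests on assumptions. That is true of the size. The point itself still stands: the stated method allows for neither repeated events nor a count limited to one per patient, and it miscovers on two of the three natural readings.

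The lowest coverage figures need high variance and loss unrelated to propensity. With propensity-linked deaths of 0.1 to 0.3 per year, counted as SAEs and added to the 30% loss, all-SAE coverage was 89% to 90% at r = 0.2, k = 1, and 80% to 83% at r = 0.3, k = 2. Undercoverage shrinks but remains. On the patient reading, the excess width can vanish under heavy linked mortality: the ratio of Poisson to true standard error fell to 0.96 at the extreme.

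A reader might infer that 3.5.3.3 contradicts 3.5.5.3. It does not: the proportion of patients and the person-year rate are listed as separate parameters. A reader might also infer that the plan breaks its own rule, because 3.5.5.1.3 says "Poisson regression with generalized estimating equations will be used to evaluate the effect of the vaccine on the rates" of health-care use and work loss. That is an analogy for handling repeated counts, not an inconsistency; it concerns other endpoints and does not specify a rate-difference interval.

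Section 3.5.6 warns that "caution should be exercised when interpreting the results" for adverse-experience comparisons. The warning is about multiplicity, not an understated variance, but it does discourage reading one interval as a test. The interval has no decision rule, and SAEs are also listed by patient.

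**Conclusion.** The point holds as a minor one. Section 3.5.5.3 prescribes a plain Poisson interval without defining what is counted or over what time. If all SAEs are counted over total follow-up, the interval is too narrow whenever propensity varies: roughly 82% to 93% coverage under the assumed rates of 0.1 to 0.3 and variance of 0.5 to 1, lower at higher variance, and less is lost if drop-out or death tracks propensity. If patients are counted over total follow-up, it is generally too wide.

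It would go too far to say that the plan's interval is anti-conservative as written, or that the trial's safety conclusions are unsound. The direction depends on a definition that the documents do not give. The primary safety endpoint (SAEs to 28 days after dose 4) uses binomial methods. That endpoint, death and efficacy are unaffected, and the effect on rare vaccine-related SAEs is negligible.

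**What to change.** In 3.5.5.3, before unblinding, state whether the numerator is all SAEs or patients with at least one SAE, and over what time at risk. Compute the CI for the all-cause SAE rate difference with the patient-level robust (sandwich) variance given above. Keep the Poisson method for death and, where rare, for vaccine-related SAEs.

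Counting first SAEs with person-time stopped at the event, and keeping the Poisson method, is a second choice. It changes the estimand, discards repeat SAEs, and its coverage can fall to about 91% to 93%.

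The cost is a sentence or two of text; the data are already collected and the software is standard. The price is a wider all-SAE interval where propensity varies (+16% to +30% at 0.2 per person-year with variance 0.5 to 1), and no material change where it does not. Section 3.5 already provides for "Changes to exploratory or other non-confirmatory analyses made after the protocol has been finalized", to be explained in the study report, so a later change is permitted. Fixing the unit while the data are still blinded avoids a choice made with the results in view.

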### 3.5.6 Multiplicity

With the decision made from the first interim futility analysis (provided in Sections 1.3 and 1.4), there is only one efficacy analysis performed for the primary efficacy hypothesis in the STM population. As no population enrichment is planned, no multiplicity adjustment will be made for primary efficacy analysis in the STM population and the primary efficacy hypothesis will be tested at one sided  $\alpha=0.0125$ .

No multiplicity adjustment will be made for the analyses related to the secondary objective and exploratory objectives, including any analyses related to immunogenicity, due to their exploratory nature.

For comparisons of adverse experiences between the vaccine and placebo groups, the goal is to investigate if there exists an overall trend of risk difference between the 2 groups. It is recognized that there exists a multiplicity issue for conducting multiple comparisons on these items, with each comparison being performed at the two-sided 0.05 level (corresponding to the 95% CI). Since the overall significance level for these comparisons will be much  $>0.05$ , caution should be exercised when interpreting the results.

### 3.5.7 Sample Size and Power

#### 3.5.7.1 Efficacy Analysis

This is an event-driven study. With a 1:1 randomization ratio between the vaccine and placebo groups and a total of 90 HZ cases in the STM population with 2696 patients, the study will have an overall power of ~84.2% to detect 65%  $VE_{HZ}$  at the overall two-sided 0.025 significance level, based on the success criterion of the lower bound 97.5% CI for  $VE_{HZ}$  being greater than 25%. Table 3-3 also provides power for a variety of assumed vaccine efficacy.

Table 3- 3 Power for Primary Efficacy in the STM Population with 90 Cases

Cases	Power at assumed vaccine efficacy (VE)					
	VE=80	VE=75	VE=70	VE=65	VE=60	VE=55
90	99.9%	99.2%	95.0%	84.2%	66.6%	46.7%

To accrue ~90 confirmed HZ cases in the STM population during the time period from enrollment through approximately the end of maximum 5 years postvaccination, enrollment of approximately 2696 patients (1348 receiving vaccine and 1348 receiving placebo) will be required, assuming 1) 30% total lost-to-follow-up, 2) an HZ rate of 17 per 1000 in the placebo group, 3)  $VE_{HZ}=65\%$ , and 4) 36 months of study enrollment. The sample size calculation follows the methods described in Lachin [21].

The dropout rates and the HZ event rates will be monitored on an ongoing basis using the blinded database. If the observed HZ case accrual rate indicates that more than 5 years of patient follow-up will be necessary to accrue the targeted number of confirmed cases, then the SPONSOR will consider it beyond the adjustment cap and terminate the study without extended follow-up time and increasing enrollment. Because of the event driven design, no additional interim analysis is expected to be performed when follow-up time is extended or when enrollment is increased. Should enrollment increase, patients enrolled under this scenario will also be followed for safety and efficacy for at least 1 year following receipt of their last dose of V212 or placebo.

Since the incidence of clinically significant pain, complications as defined by the composite secondary endpoint and PHN are unknown in this population, formal hypothesis testing for these secondary endpoints will not be performed, but rather the analysis will focus on the estimation of the vaccine efficacy on these endpoints. To quantify the precision of the analysis, as an example, if the underlying true vaccine efficacy for any one of these secondary endpoints is 52%, and 10% of HZ cases developed a secondary endpoint for vaccine and placebo group, then at interim and final analysis where the HZ case split between vaccine and placebo has met the statistical success criterion for the primary hypothesis, the point estimates and CIs (adjusting for multiplicity) on the secondary endpoints efficacy are roughly 50% (-80%, 88%) and 40% (-50%, 77%), respectively. If 20% of HZ cases developed a secondary endpoint, then the above point estimates and CIs are 48% (-24%, 80%) and 44% (-1%, 71%), respectively. If 40% of HZ cases developed a secondary endpoint, then the above point estimates and CIs are 48% (5%, 72%) and 43% (11%, 64%), respectively.

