#### **2.1.3 Secondary Objectives**

1. To assess the impact of V212 on the development of moderate to severe HZ-associated pain at any time from HZ onset through the end of the 6 month HZ follow-up period. Moderate to severe HZ-associated pain is defined as 2 or more occurrences of a score of 3 or greater (0-to-10 scale) on the Zoster Brief Pain Inventory (ZBPI).
2. To assess the impact of V212 on the development of HZ complications defined as the occurrence of any of the following during the study: hospitalization or prolongation of hospitalization due to HZ, disseminated HZ (including disseminated HZ rash or VZV viremia), visceral HZ, ophthalmic HZ, neurological impairment due to HZ, or administration of intravenous acyclovir therapy for treatment of HZ.
3. To assess the impact of V212 on the development of PHN. PHN is defined as a worst pain score (in the previous 24 hours) of 3 or greater (0-to-10 scale) on the ZBPI, that persists or appears greater than or equal to 90 days after the onset of HZ rash.

The above objectives will be evaluated for STM only.

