### 3.5.5.1.2 Analysis of Vaccine Efficacy on Secondary Efficacy Endpoints

Three secondary efficacy endpoints are defined for the STM population and in the HM population on an exploratory basis.

Since the incidences of moderate to severe HZ-associated pain, HZ-complications as defined by the composite endpoint, and PHN are unknown in this population, formal hypothesis testing for these secondary endpoints will not be performed. The incidence of the secondary efficacy endpoints of moderate to severe HZ-associated pain, composite complication endpoint, and the incidence of PHN, defined as pain in the area of the HZ rash with a “worst pain in the last 24 hours” score of 3 or greater (on a 0 to 10 scale) on the ZBPI that persists or appears greater than or equal to 90 days after HZ onset, (point estimate and 95% CI) will be compared between vaccine and placebo groups using Cox proportional hazards regression stratified by age (< 50 years of age versus  $\geq$  50 years of age) based on the MITT population. For patients who develop PHN, the PHN event onset will be the date of HZ rash onset. Patients who do not develop PHN will be considered as censored at the stop date of their HZ surveillance. Furthermore, the count and proportion of each component of the secondary efficacy composite endpoint among all randomized patients in the vaccine and placebo groups will be summarized.

Sensitivity analyses for vaccine efficacy on PHN based on alternative definitions [pain in the area of the HZ rash with a “worst pain in the last 24 hours” score of 3 or greater (on a 0 to 10 scale) on the ZBPI that persists or appears more than 30, 60, 120, and 180 days after HZ rash onset] will be compared between the vaccine and placebo groups in the MITT population.

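### The secondary-endpoint precision paragraph in 3.5.7.1 still describes a superseded design and promises narrower intervals than 90 STM cases can give

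*Combined protocol and SAP*

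**What the plan says.** The second half of section 3.5.7.1 is current text, not part of the superseded material kept in Appendix 6.3. It supposes a true secondary efficacy of 52% and that 10%, 20% or 40% of HZ cases, in both groups, develop a secondary endpoint. It then gives results "at interim and final analysis where the HZ case split between vaccine and placebo has met the statistical success criterion for the primary hypothesis". For the 10% share, "the point estimates and CIs (adjusting for multiplicity) on the secondary endpoints efficacy are roughly 50% (-80%, 88%) and 40% (-50%, 77%), respectively". The final-analysis values for the 20% and 40% shares are 44% (-1%, 71%) and 43% (11%, 64%).

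The rest of the current plan differs:

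- Size and criterion (3.5.7.1, immediately before): power is computed for "a total of 90 HZ cases in the STM population with 2696 patients", "based on the success criterion of the lower bound 97.5% CI for" vaccine efficacy exceeding 25%.
- Number of analyses (3.5.6): "there is only one efficacy analysis performed for the primary efficacy hypothesis in the STM population". Section 3.1.2 and Appendix 6.3 say that the second interim, the only one with an efficacy look, will not be held.
- Multiplicity (3.5.6): "No multiplicity adjustment will be made for the analyses related to the secondary objective and exploratory objectives".
- Intervals (3.5.5.1.2): secondary endpoints ("point estimate and 95% CI) will be compared between vaccine and placebo groups using Cox proportional hazards regression").
- Population (2.1.3): "The above objectives will be evaluated for STM only".

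**The concern.** Two things look wrong. First, the paragraph reports an interim result after efficacy success and multiplicity-adjusted intervals. The current plan contains neither, and the interim that was held in October 2014 was for futility only.

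Second, the final estimates do not fit the design. If the same share of HZ cases has a secondary endpoint in each group, secondary efficacy equals HZ efficacy apart from rounding. Final values of 40% to 44% therefore imply an HZ efficacy of about that size, and at 90 cases this looks too low to meet the criterion that the paragraph takes as met.

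The secondary endpoints are not formally tested, so the plan rests on estimating them. Section 3.5 says that no separate SAP will be issued, which makes this paragraph the only statement of how precise those estimates will be.

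**Working it through.** **Inputs.** 90 cases, 1:1 allocation, null efficacy 25% and one-sided alpha 0.0125 (2.1.2, 3.5.7.1); endpoint shares of 10%, 20% and 40%, equal in both groups (3.5.7.1); unadjusted 95% intervals (3.5.5.1.2). Equal person-time in the two groups is assumed.

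**Method.** Given n cases, vaccine cases X ~ Binomial(n, p) with p = (1 - VE)/(2 - VE). Exact (Clopper-Pearson) limits for p convert by VE = 1 - p/(1 - p). Wald limits use the log of the case ratio x/y with standard error sqrt(1/x + 1/y).

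**Step 1: reproduce Table 3-3.** Under the null, p = 0.75/1.75 = 0.4286. P(X ≤ 27) = 0.0083 and P(X ≤ 28) = 0.0149, so success needs X ≤ 27. P(X ≤ 27) at VE 80, 75, 70, 65, 60 and 55% is 99.9, 99.2, 95.0, 84.2, 66.6 and 46.7%. All six agree with the table, so 27:63 is the rule behind the plan's own power figures.

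**Step 2: which HZ splits succeed at 90 cases?**

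| Split | VE | Lower 97.5% bound, exact | Wald | Above 25%? |
|---|---|---|---|---|
| 27:63 | 57.1% | 27.4% | 28.2% | yes |
| 28:62 | 54.8% | 23.9% | 24.8% | no |
| 32:58 | 44.8% | 8.3% | 9.6% | no |
| 34:56 | 39.3% | -0.4% | 1.2% | no |

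**Step 3: precision at the 27:63 boundary, 95% intervals.** The shares give 2.7:6.3, 5.4:12.6 and 10.8:25.2 events. The 20% share can be rounded two ways.

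| Share | Events | VE | Exact | Wald | Stated final |
|---|---|---|---|---|---|
| 10% | 3:6 | 50% | (-134%, 92%) | (-100%, 87%) | 40% (-50%, 77%) |
| 20% | 5:13 | 62% | (-15%, 89%) | (-8%, 86%) | 44% (-1%, 71%) |
| 20% | 6:12 | 50% | (-44%, 85%) | (-33%, 81%) | 44% (-1%, 71%) |
| 40% | 11:25 | 56% | (7%, 80%) | (11%, 78%) | 43% (11%, 64%) |

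**Step 4: relative width.** Width on the log rate-ratio scale is ln[(1 - lower)/(1 - upper)]. The stated final intervals have widths ln(1.50/0.23) = 1.875, ln(1.01/0.29) = 1.248 and ln(0.89/0.36) = 0.905. Ratios of recomputed to stated width, exact and Wald, are:

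- 3:6: 1.79 and 1.48
- 5:13: 1.90 and 1.65
- 6:12: 1.79 and 1.57
- 11:25: 1.72 and 1.57

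**Step 5: events that the stated widths would need.** Read as 95% Wald intervals, width = 2 × 1.96 × sqrt(1/x + 1/y). Solving at the stated estimates gives about 19, 43 and 81 secondary events. Ninety cases supply 9, 18 and 36.

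**Step 6: likely origin (inference).** Table 3-8 in Appendix 6.3 gives the boundaries of the old combined HM+STM study: 59:115 at two-sided 0.02 (interim) and 83:149 at 0.044 (final). Exact intervals from these splits are:

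| Analysis, share | Events | Computed | Stated |
|---|---|---|---|
| Interim 10% | 6:12 | 50% (-71%, 88%) | 50% (-80%, 88%) |
| Interim 20% | 12:23 | 48% (-24%, 80%) | 48% (-24%, 80%) |
| Interim 40% | 24:46 | 48% (5%, 72%) | 48% (5%, 72%) |
| Final 10% | 9:15 | 40% (-50%, 77%) | 40% (-50%, 77%) |
| Final 20% | 17:30 | 43% (-8%, 71%) | 44% (-1%, 71%) |
| Final 40% | 34:60 | 43% (11%, 64%) | 43% (11%, 64%) |

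Four of six agree. The interim 10% entry differs in the lower limit, and the final 20% entry in the lower limit and, by one point, the estimate. The old STM-only boundary does not fit: its final split of 72:138 gives 7:14 at a 10% share, or 50% (-56%, 86%). If the combined origin is right, the final 40% example uses 34 + 60 = 94 secondary events, more than the 90 HZ cases now planned.

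**The case against.** The best defence is that the paragraph is an illustration, hedged as an example with rough figures, and that nothing depends on it. The secondary endpoints carry no formal test, so strictly an estimate of 40% cannot fail a criterion that applies to HZ incidence. No sample size, alpha or procedure depends on it, and the reported intervals will come from the data.

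There are technical points too. The replacement values are for the barest success, whereas the text covers any split that meets the criterion. The planned stratified Cox analysis could move the cut by about one case. Exact limits are harsher than the Cox analysis is likely to be: by Wald at the 40% share the lower limit is 11%, as stated. The origin in Table 3-8 is not proven, since two of the six entries do not reproduce.

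Much of this stands as limits on the claim. The failure is indirect, through the equal shares that the paragraph itself assumes. The replacement figures are illustrative, and the effect is confined to a descriptive statement. None of it rescues the text. Splits beyond 27:63 have higher efficacy, further from 40% to 44%. A one-case shift leaves the threshold near 55%. Wald intervals are still about 1.5 to 1.65 times as wide as stated. The conflict with 3.5.6 and 3.5.5.1.2 needs neither the origin nor any calculation.

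**Conclusion.** The concern holds. The paragraph describes an interim efficacy result and a multiplicity adjustment that the current plan does not have. Its final estimates imply an HZ efficacy that would miss the primary criterion at 90 cases: the boundary is 57%, and a split near 44% has a lower bound of only about 8% to 10%. Its final intervals correspond to roughly twice the secondary events that 90 cases would supply.

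The overstatement of precision is largest for a rare endpoint, where the exact lower limit moves from -50% to -134% (-100% by Wald). At the 40% share the lower limit hardly changes, and the main difference is in the estimate and the upper limit. These figures assume equal person-time, equal endpoint shares and a split on the success boundary. Primary power, the primary test and the secondary analysis rules are unaffected. It should be corrected, but it does not threaten the trial's main inference.

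**What to change.** Recompute the paragraph in 3.5.7.1 for one final analysis of 90 STM cases with unadjusted 95% intervals, consistent with 3.5.5.1.2 and 3.5.6. State the HZ split assumed, how event counts are rounded, and whether the limits are exact or Wald. Showing the expected split at the design efficacy of 65% beside the 27:63 boundary would help the reader. Remove the interim values and the reference to multiplicity adjustment. Any assumed secondary efficacy may be used if it is stated and agrees with the split shown.

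The same edit could clear two related remnants: the sentence in 2.7.1 on adjusting for planned interim analyses, and the mention in 3.2.19 of a successful interim efficacy analysis.

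The cost is a wording change. Sample size, testing and conduct stay as they are; the stated intervals become wider.
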